10.4 Analysis of Secondary Endpoints

1. To Identify tumor dose response thresholds (TDRT) and tumor dose distribution in patients with HCC treated with Y90 resin microspheres.

All patients will undergo baseline liver mass protocol abdominal MRI without and with contrast within 30 days prior to the shunt study, and 1, 3, 6, and 12 months after Y90 RE therapy.

Objective TR will be evaluated longitudinally using mRECIST criteria by [name] with a help of an abdominal radiologist. TDR will be calculated using two different methods: 1. Mean dose of the entire tumor resulting in objective TR; 2. Determination of % tumor volume receiving >100 Gy resulting in objective TR. The reason for the second TDR calculation is to take into account the non-homogeneity of Y90 dose delivered to the tumors previously reported.[27, 28] TDR threshold based on logistic regression will be determined by Drs. [name], [name], and [name].

2. To optimize low dose Y90 techniques in predicting TNR and LSF.

No statistical consideration was deemed necessary for this secondary endpoint.

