8. STUDY ASSESSMENTS AND PROCEDURES

All patients will undergo baseline liver mass protocol abdominal MRI without and with contrast within 30 days prior to the shunt study, and 1, 3, 6, and 12 months after Y90 RE therapy.

Objective TR will be evaluated longitudinally using mRECIST criteria by [name] with a help of an abdominal radiologist. TDR will be calculated using two different methods: 1. Mean dose of the entire tumor resulting in objective TR; 2. Determination of % tumor volume receiving >100 Gy resulting in objective TR. The reason for the second TDR calculation is to take into account the non-homogeneity of Y90 dose delivered to the tumors previously reported.[27, 28] TDR threshold based on logistic regression will be determined by Drs. [name] and [name].

Additional scan assessments may be collected based on clinical symptoms, as appropriate. Documented tumor measurements are required using CT scans, MRI, physical examination, and/or digital photography, as appropriate. Any imaging used to assess disease at any time point will be submitted for an independent radiology review. The same method of assessment (CT or MRI and/or digital photography) and the same technique for acquisition of images must be used for all

study assessments (contrast must be used unless medically contraindicated). Baseline imaging should be done at the same institution/facility which will be used to measure response during the patient's participation in the study. Radiographic assessments and efficacy analyses will be conducted by the Investigator site as well as the independent radiology review committee.

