3:00 PM-3:30 PM: Removal of the radial sheath at IR post procedural area and discharge.

4:30-5:30 PM: Y90 PET/CT at Cardiac PET center on the 4th floor of EUHM.

Patient is free to go home after this.

K. Y90 Therapy Tumor, Liver, and Lung Dose Calculation (Friday)

Utilizing the MIM software, post Y90 therapy PET/CT data and partition method described above, the mean actual dose delivered to the tumor, normal liver, and lung will be calculated by Drs. [name] and [name]. The software will generate ROIs from the inside to the periphery of the tumor based on Y90 delivery, and Dose Volume Histograms (DVH) plotting the delivered dose as a function of liver volume. Using DVH, % of tumor volume receiving >100Gy and dose range to the tumor will be also calculated.

L. Follow-up phone call [REDACTED] or study nurse (1-week post therapy)

Patient will be followed by phone to ensure they are doing well, and they will be screened for any symptoms related to adverse events. If any concerning symptoms is reported, they will be brought to IR clinic for further evaluation.

M. 1-Month clinical and Imaging Follow-up

- Multiphase liver mass protocol MRI or CT will be obtained
- Brief medical history
- Symptom-directed physical exam
- ECOG Performance Status
- Vitals signs
- Review of prior/concomitant medications
- Clinical laboratory tests for:
 - Hematology
 - CMP

N. 3-Month clinical and Imaging Follow-up

- Multiphase liver mass protocol MRI or CT will be obtained
- Brief medical history
- Symptom-directed physical exam
- ECOG Performance Status
- Vitals signs
- Review of prior/concomitant medications
- Clinical laboratory tests for:
 - Hematology
 - CMP

O. 6-Month clinical and Imaging Follow-up

- Multiphase liver mass protocol MRI or CT will be obtained
- Brief medical history
- Symptom-directed physical exam
- ECOG Performance Status

- Vitals signs
- Review of prior/concomitant medications
- Clinical laboratory tests for:
 - Hematology
 - CMP

End of Treatment

End of treatment is defined as the last planned Y90 therapy within the 6-month dosing period. For subjects who discontinue drug treatment prior to 6 months, end of treatment is considered the last visit where the decision is made to discontinue treatment. All required procedures may be completed within \pm 7 days of the end of treatment visit. Repeat disease assessment is not required if performed within 28 days prior to the end of treatment visit.

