characterize any objective tumor regression in the measurable dimension of the disease. All other lesions (or sites of disease) including pathological lymph nodes should be identified as non-target lesions and should also be recorded at baseline. Measurements are not required and these lesions should be followed as ‘present’, ‘absent’, or in rare cases ‘unequivocal progression’. For assessment of abscopal response, any of the target lesions identified at baseline will be measured and followed for abscopal response. This target lesion should not be a target of injection or biopsy. The abscopal response is defined as a shrinkage of $\geq 20\%$ from baseline in any target non-manipulated metastatic lesion identified at baseline.

Evaluation of Target Lesions

Complete Response (CR): No intramural arterial enhancement in all target lesions.

Partial Response (PR): At least a 30% decrease in the sum of the diameters of viable (enhancement in the arterial phase) target lesions.

Progressive Disease (PD): At least a 20% increase in the sum of the diameters of viable target lesions.

Stable Disease (SD): Features classifiable as neither partial response nor progressive disease.

Evaluation of Non-Target Lesions

Complete Response (CR): No intramural arterial enhancement in all target lesions.

Partial Response (PR): At least a 30% decrease in the sum of the diameters of viable (enhancement in the arterial phase) target lesions.

Progressive Disease (PD): At least a 20% increase in the sum of the diameters of viable target lesions.

Stable Disease (SD): Features classifiable as neither partial response nor progressive disease.

Although a clear progression of “non-target” lesions only is exceptional, the opinion of the treating physician should prevail in such circumstances, and the progression status should be confirmed at a later time by the review panel (or Principal Investigator).

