The duration of overall CR is measured from the time measurement criteria are first met for CR until the first date that progressive disease is objectively documented.

Duration of stable disease: Stable disease is measured from the start of the treatment until the criteria for progression are met, taking as reference the smallest measurements recorded since the treatment started, including the baseline measurements.

Progression-Free Survival

PFS is defined as the time from the date of first dose to the date of the first objectively documented progressive disease per m-RECIST or death, whichever is earlier. Patients who do not have the date of disease progression per m-RECIST or date of death will be censored on the date of the last evaluable tumor assessment. Patients who started a new antineoplastic regimen prior to disease progression per m-RECIST will be censored on the date of the last evaluable tumor assessment prior to receiving the new antineoplastic regimen. Patients whose disease progression or death appears after missing two consecutive tumor assessments will be censored on the date of the last evaluable tumor assessment. Patients who are lost to follow up will be censored on the date of their last evaluable tumor assessment. PFS will be estimated using the Kaplan-Meier method. The median and its 95% CI, along with the 25% and 75% quartiles will be summarized for all treated patients. OS will be defined as the date of first dose to the date of death. Patients who do not have a date of death will be censored on the last date for which the patient was known to be alive. OS will be analyzed similarly to PFS.

Response Review

All responses will be reviewed by an expert(s) independent of the study simultaneously as the results become available.

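### The plan does not say which mRECIST read feeds the tumor dose-response threshold, and states no masking of the named reader to delivered dose, although an independent review of all imaging is already planned

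*Combined protocol and SAP*

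**What the plan says.** Section 10.4, under the TDRT objective, states: "Objective TR will be evaluated longitudinally using mRECIST criteria". The sentence goes on to assign this to one named person, assisted by an abdominal radiologist. Section 8 repeats the sentence. In both places the response is then related to tumor dose in two ways (mean dose, and percent of tumor volume above 100 Gy), and the threshold comes from logistic regression.

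Delivered dose is calculated earlier. Section 8.1, item K, has two named study doctors compute it from the post-therapy PET/CT on the Friday of therapy week. The first response imaging is at 1 month.

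An independent review is also planned. Section 8 states: "Any imaging used to assess disease at any time point will be submitted for an independent radiology review". It adds: "Radiographic assessments and efficacy analyses will be conducted by the Investigator site as well as the independent radiology review committee". The response review paragraph at the end of Section 9.1.2 says: "All responses will be reviewed by an expert(s) independent of the study simultaneously as the results become available".

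Section 10.5.4 defines TDRT as the dose that results in CR or PR. It defines LD 50 and LD 70 from the tumor volume receiving more than TDRT, and relates them to response. Section 10.5.3 gives the response-rate analysis. None of these sections says whose read supplies CR or PR.

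**The concern.** mRECIST depends on measuring the enhancing part of the tumor, and after radioembolization that involves judgement at the margins. If the person making a borderline call knows the tumor received a high or low dose, the call may drift toward what the dose suggests. The TDRT analysis regresses exactly that call on exactly that dose, so such drift acts directly on the slope and hence on the threshold. LD 50 and LD 70 inherit the problem twice, because they use TDRT as their cut and are then correlated with response.

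The second issue needs no assumption about reader behaviour. Two sets of responses will exist, and the plan does not say which one counts. The choice could be made after both results are known. Section 2.1 itself attributes much of the spread in published thresholds to differences in dosimetry methodology. An unspecified response read would add another source of variation.

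**Working it through.** **Step 1: set the sections side by side.**

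| Question | Where | Answer in the plan |
|---|---|---|
| Who reads response for TDRT? | 8, 10.4 | A named reader with an abdominal radiologist |
| When is dose known to the study team? | 8.1 item K | Friday of therapy week, before any response scan |
| Is the reader masked to dose? | none | Not stated |
| Is there an independent read? | 8, 9.1.2 | Yes, all disease imaging and all responses |
| Who runs efficacy analyses? | 8 | The site and the independent committee |
| Which read gives CR/PR for TDRT and LD 50/LD 70? | 10.4, 10.5.4 | Not stated |
| How are discordant reads handled? | none | Not stated |

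I take the named reader to be the site read, because Section 8 treats the independent committee separately.

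**Step 2: illustrate the size.** The plan gives no figure to reproduce. The inputs below are assumptions except n = 30 (Section 10.2).

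- One tumor and one dose value per patient; true response 50-60% and unrelated to dose.
- Model: logit P(CR or PR) = a + b × dose, with the slope b tested at a nominal two-sided 0.05.
- A read disagrees with dose if it is a non-response above the center of the dose distribution or a response below it. A share f of such reads is tipped to agree.
- With true response rate p, expected tipped reads = 30 × [0.5(1 − p) + 0.5p] × f = 15f.

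False-positive rate for the slope:

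| f | Expected tipped reads of 30 | Slope test, split at median dose, response 50-60% (8,000 trials) | Logistic likelihood ratio, split at mean dose, response 50% (3,000 trials) | Median odds ratio per SD of dose, likelihood-ratio runs |
|---|---|---|---|---|
| 0 | 0 | 5% | 6.0% | 1.01 |
| 5% | 0.75 | not run | 6.8% | 1.09 |
| 10% | 1.5 | 7-8% | 8.8% | 1.19 |
| 15% | 2.25 | 10% | not run | not run |
| 20% | 3 | 14% | 16.3% | 1.42 |
| 30% | 4.5 | 25-27% | 27.6% | 1.71 |

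A likelihood-ratio version with the median split and 50-60% response gives 6% at f = 0 and 16-17% at f = 20%. For f between 10% and 20% the range over these versions is therefore about 7-17%, against 5-6% with no tipping.

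**Step 3: check the effect on the overall response rate.**

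- Net change = 0.5(1 − p)f − 0.5pf.
- p = 0.5: the two terms cancel.
- p = 0.6, f = 0.15: 0.5 × 0.4 × 0.15 − 0.5 × 0.6 × 0.15 = 3.0 − 4.5 = −1.5 percentage points.
- p = 0.6, f = 0.20: 4.0 − 6.0 = −2.0 points.
- Standard error of the rate at n = 30: √(0.6 × 0.4 / 30) = 8.9 points.

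The response rate hardly moves. The effect falls on the slope.

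**The case against.** The best defense is that Section 8 gives the independent committee a part in the efficacy analyses and not merely in re-reading scans, and Section 9.1.2 has every response reviewed independently. An independent TDRT analysis may therefore be intended. That narrows the point: what is missing is a precedence rule, not an independent analysis. It does not remove the point, because two analyses without a stated order leave the choice open, and 10.4 mentions only the named reader.

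The simulation can also be challenged. The plan specifies no test or alpha for the dose slope, only a threshold from logistic regression. The tipping pattern is one that produces a slope, and Section 5.1 allows up to three lesions per patient. All of this stands. The figures show direction and rough sensitivity, and they do not measure bias in the threshold itself.

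Three stronger readings are tempting but not supported:

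- **That the response reader knows the dose.** Names are removed, so it cannot be established that the reader and the dose calculators are the same people, or that the radiologist sees the dosimetry. The documents are silent on masking; they do not describe dose-aware reading.
- **That response rates are materially biased.** Step 3 of the working shows otherwise under this mechanism.
- **That the non-target progression clause in Section 9.1.1, where "the opinion of the treating physician should prevail in such circumstances", undermines TDRT.** The same sentence provides for later confirmation by the review panel or Principal Investigator. It concerns exceptional progression of non-target lesions, and so barely bears on CR or PR. No change to it is needed for this point.

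**Conclusion.** The point holds in a limited form. The plan ties the TDRT response to a named reader with no stated masking to dose. It also plans an independent read of the same scans, and does not say which read governs TDRT and LD 50/LD 70 or how disagreements are handled. The missing precedence rule is a matter of record and rests on no assumption.

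The possible bias is conditional on dose-aware reading. If 10-20% of reads that disagree with dose were tipped (about 1.5 to 3 reads in 30), the false-positive rate for the slope would rise from about 5-6% to about 7-17%. This assumes one tumor per patient, 50-60% response, no true dose effect and symmetric tipping. The documents give no tipping rate.

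TDRT is a secondary objective. The primary comparison of LSF and TNR does not use tumor response and is unaffected. The change is nonetheless worth making early, because masking cannot be restored once scans have been read with the dose known.

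**What to change.** - In 10.4 and 10.5.4, state that the independent review's mRECIST read, made without access to dosimetry, is the response variable for TDRT and LD 50/LD 70. For consistency, name the same read for the response rate in 10.5.3.
- State that the independent read governs where the two differ, and that the site read is used as a sensitivity analysis only.
- Lock the dose file from the therapy-week calculation before the 1-month scan is read.

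The cost is SAP wording and withholding dosimetry from a review that is already planned. No additional scan or reader is required. The downside is that the two reads may differ, and both results must then be reported.

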9.1.1 Tumor response evaluation

To assess objective response or future progression, it is necessary to estimate the overall tumor burden at baseline and use this as a comparator for subsequent measurements. Measurable disease is defined by the presence of at least one measurable lesion.

When more than one measurable lesion is present at baseline, all lesions up to a maximum of 3 lesions total in the targeted liver lobe and 3 lesions in the non-target liver lobe and additionally 3 lesions outside of liver will be evaluated. We will use m-RECIST for the evaluation of liver lesions which is based on the size of enhancing portion of the lesions and not the entire size of the lesion. This has shown to be much more accurate in evaluation of HCC compared to RECIST and RECIST 1.1 [42].

Target lesions should be selected on the basis of their size (lesions with the longest diameter), be representative of all involved organs, but in addition should be those that lend themselves to reproducible repeated measurements. It may be the case that, on occasion, the largest lesion does not lend itself to reproducible measurement in which circumstance the next largest lesion which can be measured reproducibly should be selected. Pathological nodes which are defined as measurable and may be identified as target lesions must meet the criterion of a short axis of ≥ 15 mm by CT scan. Only the short axis of these nodes will contribute to the baseline sum. All other pathological nodes (those with short axis ≥ 10 mm but < 15 mm) should be considered non-target lesions. Nodes that have a short axis < 10 mm are considered non-pathological and should not be recorded or followed. If lymph nodes are to be included in the sum, then as noted above, only the short axis is added into the sum. The baseline sum diameters will be used as reference to further

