10.5.4 Analysis of secondary endpoints

Secondary clinical endpoints will be evaluated to assess outcomes including biology of resistance and survival. The endpoints with their definitions are listed as follows:

1. Tumor Dose Response Threshold (TDRT): defined as the Y90 dose that results in CR or PR
2. Tumors with LD 50 and LD 70: Defined at frequency of tumors in which 50% or more or 70% or more of their volume received above TDRT and their correlation with response.
3. Time to progression (TTP): defined as the time from start of protocol therapy until the criteria for disease progression are met. Patients who are either lost to follow-up, die or who begin alternative treatments prior to progression, will have their data censored as of the date considered to be lost to follow-up, date of death, or the first day of alternative therapy.
4. Progression-free survival (PFS): defined as the time from start of protocol therapy to disease progression or death from any cause, censoring patients without an event at time of last clinical assessment.
5. Overall survival (OS): defined as the time from start of protocol therapy to death, censoring patients who are alive at last follow-up

Protocol therapy related toxicities rate will be summarized using descriptive statistics such as frequencies and proportions. Differences in the proportion of patients who experience protocol-related toxicities will not be compared between cohorts.

To compare TDRT and Tumors with LD 50 and LD 70 between two groups, two sample paired t-tests will be conducted when data followed a normal distribution, otherwise Wilcoxon signed rank test will be used instead. General linear model (GLM) will be further used in the multivariable analysis to estimate the adjusted efficacy of treatment (MAA vs Y90) on TDRT and Tumors with LD 50 and LD 70 after adjusting for other factors, respectively. Pearson correlation coefficients will be calculated to measure the correlation between two numerical variables, and the significance of coefficients will be tested using Wald's test.

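### The tumor dose-response analyses fix neither unit nor response time point and make no allowance for several lesions and readings per patient; if tumors are the unit, uncertainty is understated

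*Combined protocol and SAP*

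**What the plan says.** Section 10.4 (repeated in Section 8) gives two dose measures: "Mean dose of the entire tumor resulting in objective TR" and "Determination of % tumor volume receiving >100 Gy resulting in objective TR". On the model it says only "TDR threshold based on logistic regression will be determined by" named team members. On the outcome it says "Objective TR will be evaluated longitudinally using mRECIST criteria".

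Section 10.5.4 adds "Tumor Dose Response Threshold (TDRT): defined as the Y90 dose that results in CR or PR". LD 50 and LD 70 are "Defined at frequency of tumors in which 50% or more or 70% or more of their volume received above TDRT", together with their correlation with response. For TDRT and LD 50/LD 70 it names paired t-tests or signed rank tests, a general linear model, and Pearson correlations with Wald tests.

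Section 5.1 admits patients with up to 3 lesions, and Section 9.1.1 evaluates "all lesions up to a maximum of 3 lesions total in the targeted liver lobe".

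No section says what one row of the logistic model is, which visit or best response supplies the outcome, or how several lesions or visits in one patient are handled.

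**The concern.** Lesions in one patient lie in a single lobe (Section 5.1) and are treated from the hepatic artery branch supplying them (Section 7.1.2), so their doses and responses are likely to be correlated. Delivered dose does not change after treatment, so a second or third reading of the same lesion adds little independent information about dose and response. A model that counts every lesion, or every lesion at every visit, as a separate observation overstates how much is known.

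TDRT is a named secondary objective. Section 2.1 itself attributes the wide spread of published thresholds largely to differences in dosimetry method. A threshold reported with too much precision would add to that spread.

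**Working it through.** The plan states no sample size, power, p-value or interval for the threshold, so there is no figure of its own to reproduce. Section 10.2 sizes the trial on LSF and TNR only.

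**1. What a row could be**

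| Reading | Support in the documents | Clustering |
|---|---|---|
| Patient | Section 9.1.1 defines PR on the sum over target lesions; Section 9.1.2 gives a best overall response per patient | None, but no rule says which lesion's dose enters |
| Lesion | Tumor-level dose (10.4); LD 50/LD 70 count tumors (10.5.4); up to 3 lesions (5.1) | Lesions within patient |
| Lesion at each visit | Longitudinal evaluation (10.4) | Lesions and visits within patient |

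**2. Approximate size**

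For the dose slope, the variance inflation is D = 1 + (m − 1) × ρy × ρx. Here m is the number of rows per patient, ρy the correlation of the yes/no responses and ρx the correlation of the doses. Across visits ρx = 1, because the dose is fixed. The standard error is too small by a factor √D.

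Assume a latent patient ICC of 0.3 or 0.5. At a response rate of one half, ρy is about (2/π) × arcsin(ICC), which is 0.19 or 0.33.

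- Three lesions, one reading, ρx = 0.5 (assumed): D = 1 + 2 × 0.19 × 0.5 = 1.19, or 1 + 2 × 0.33 × 0.5 = 1.33; √D = 1.09 or 1.15.
- One lesion, three stacked visits: D = 1 + 2 × 0.19 = 1.38, or 1 + 2 × 0.33 = 1.66; √D = 1.17 or 1.29.

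**3. Simulation with no true dose effect**

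There were 30 patients, a within-patient dose correlation of 0.5 and 1,500 runs per row. The mixed case has 1, 2 or 3 lesions in 50/30/20% of patients, a mean of 0.5 + 0.6 + 0.6 = 1.7, or about 51 lesions. The table shows the rejection rate at a nominal 5% and the median ratio of clustered to ordinary standard error. All inputs except the 30 patients and the maximum of 3 lesions are assumptions.

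| Lesions | Readings | Latent patient ICC | Ordinary | Clustered | SE ratio |
|---|---|---|---|---|---|
| 1 | 1 | 0.30 / 0.50 | 2.4% / 4.0% | 2.2% / 3.1% | 1.03 / 1.02 |
| 1–3 | 1 | 0.30 / 0.50 | 5.3% / 6.1% | 4.3% / 5.1% | 1.04 / 1.08 |
| all 3 | 1 | 0.30 / 0.50 | 7.5% / 7.8% | 5.0% / 3.7% | 1.10 / 1.15 |
| 1 | 3 stacked | 0.30 / 0.50 | 9.5% / 15.0% | 4.2% / 6.1% | 1.17 / 1.28 |
| 1–3 | 3 stacked | 0.30 / 0.50 | 13.1% / 18.5% | 5.9% / 5.1% | 1.26 / 1.42 |
| all 3 | 3 stacked | 0.30 / 0.50 | 17.7% / 24.3% | 5.9% / 5.3% | 1.38 / 1.61 |

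Adding a separate lesion effect (latent patient ICC 0.18) with three stacked readings gave 14.9% (one lesion), 16.9% (mixed) and 18.3% (all 3) for the ordinary model, and 5.0 to 5.4% with clustering. Simulation error is about 0.6 points near 5% and 1 point near 20%.

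A second set used 3,000 datasets per scenario, 51 to 57 lesions in 30 patients and latent ICC 0.23 to 0.50. It gave 5 to 9% with one reading, 12 to 24% with three stacked readings, and about 4 to 8% with clustering. In its worst example (ICC 0.5, dose ICC 0.8, three visits) the ordinary model rejected in 23.7% of runs and the clustered one in 6.4%. The ordinary standard error was 0.165 against a true 0.281, so 1 − 0.165/0.281 = 41% too small.

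**4. What was not measured**

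These figures are for the test of the dose slope. Coverage of a threshold interval was not simulated. The threshold is computed from the same intercept and slope, so the direction carries over, but not necessarily the size.

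**The case against.** A reader might infer that the plan treats lesions and visits as independent, and that the p-values and intervals of the threshold regression are therefore too optimistic. The documents do not support that. They never say rows are pooled or independent, and they specify no p-value or interval for the threshold. Evaluating response longitudinally describes the assessment, not the model.

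A patient-level reading is also open. Partial response is "At least a 30% decrease in the sum of the diameters of viable (enhancement in the arterial phase) target lesions", complete response refers to all target lesions, and the response rates in Section 10.5.3 are counted in patients. With one row per patient there is nothing to cluster. The t-tests in Section 10.5.4 are paired, so they do handle the MAA/Y90 pairing within a unit.

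The larger error rates need stacked visits. With one reading per lesion, clustering changes about 5 to 9% into about 4 to 8%, so most of the gain comes from fixing one response per lesion. The endpoint is secondary and the trial was not sized for it.

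All of this stands, and it limits the claim. It does not close the gap. A patient-level model still needs a rule for which of up to three tumor doses enters, and none is given. It also does not fit LD 50/LD 70, which count tumors. Pairing MAA with Y90 does not address several lesions in one patient.

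**Conclusion.** The point holds as a gap in specification with a conditional consequence. The unit of analysis, the response time point and the handling of several lesions and visits per patient are not stated, and nothing in the named methods supplies an allowance for within-patient correlation.

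If tumors are the unit, uncertainty is understated. The effect is modest with one reading per lesion (type I error about 5 to 9%) and substantial only if visits are also stacked as independent rows (about 12 to 24%). Repeated visits, rather than multiple lesions, drive most of the possible inflation. If one row per patient was intended, the clustering problem disappears and the missing dose rule takes its place.

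The sizes depend on assumed ICCs, dose correlations and lesion mix. The existence of the gap does not. It is worth correcting because the correction is cheap, not because the analysis as written is shown to be wrong.

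**What to change.** Amend Sections 8, 10.4 and 10.5.4 as follows.

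- Make the lesion the unit of the TDRT and LD 50/LD 70 analyses.
- Define lesion-level mRECIST response, because Section 9.1.1 defines it only across target lesions.
- Use one response per lesion: best CR or PR by 6 months. Both imaging schedules include 1, 3 and 6 months, so this works without deciding between them.
- Fit the logistic model with patient-clustered robust standard errors, or with a patient random intercept.
- Obtain the threshold confidence interval by resampling whole patients, not lesions.
- Apply the same patient clustering to LD 50/LD 70 and their association with response.

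Two conflicts must also be reconciled. Imaging is at 1, 3 and 6 months in Sections 1.3 and 9.1, but at 1, 3, 6 and 12 months in Sections 8 and 10.4. The lesion maximum is 3 in Section 5.1 and 3 in the targeted lobe in Section 9.1.1, but Section 9.1 allows up to 5 target lesions per treated lobe.

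The cost is a few sentences of text, a lesion-level response definition, a little more analysis work and slightly wider intervals. No new visits or data are needed.
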